## 2. STUDY DESIGN

We will perform a cluster randomized controlled trial with a follow-up time of 12 months.

The three participating primary care cooperatives, i.e. Nijmegen, Arnhem, and Doetinchem, will recruit 15 general practices (clusters) who will be randomized using a 2:1 ratio in two study groups:

1. The intervention group: the GDM programme including a person-centered, integrated, and holistic approach
2. The control group: care as usual according the current SDM programmes

All practices will receive instructions from the research team on the procedures of the evaluation study. Participating practices will then start recruiting patients from a random sample of eligible patients, i.e. patients with DM2, COPD, or CVD who are currently receiving SDM. After written informed consent, information will be collected through questionnaires at baseline, 6 months and 12 months, and by interviews and data collection from electronic medical records. Information will also be collected from the participating healthcare providers through questionnaires and interviews.

In the two months prior to the start of the intervention, all practices in the intervention group will be trained in providing GDM by their own primary care cooperative. During follow-up two to three intervention meetings will take place including peer coaching and case study discussions.

Practices who are allocated to the usual care group will not receive any training, but will continue with their SDM programmes.

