Because we value each aim (population health and patient experience) as equally important, we are using a composite primary outcome, which consist of the percentage of patients who have a clinically relevant improvement of at least the minimal clinically important difference (MCID), defined as  $0.5 \times \text{SD}$  of the baseline mean, in either the PROMIS GMH score OR the PROMIS GPH score OR the P3CEQ-score AND who experience no decrease of at least the MCID in either the PROMIS GMH score OR the PROMIS GPH score OR the P3CEQ-score.

In our recent pilot study [unpublished] we followed 98 patients who received our intervention for six months. Of the 79 patients who completed all questionnaires, we found that in 30.4% of the patients the requirements for a positive score on the composite primary outcome were met. Loss to follow-up was 20%. Based on these results and the longer duration of intervention in the evaluation study (12 months vs 6 months), we hypothesised that in the evaluation study 35% of the intervention patients compared to 20% of the usual care patients will improve more than  $0.5 \times$  the expected SD of baseline mean on one of the scores at 12 months, and show no decrease of the MCID on the other scores. We estimate that we need a total sample size of 680 patients (17 practices with an average of 40 patients per practice) to detect a difference of 15% between the control and intervention group, taken into account an alpha level of 5%, a power of 80%, an intra-class correlation coefficient (ICC) of 0.03 [15], and a loss to follow-up of 20%.

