#### 4.6 Follow-up of subjects withdrawn from treatment

For intention-to-treat analyses all available data from patients will be used. Patients who withdraw will be asked to fill the questionnaire for the measurement of the primary outcomes at 12 months.

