### 6. STATISTICAL ANALYSIS

Data analysis will be performed according to the intention-to-treat principle. Data from patients who discontinued follow-up will be included in the analysis up to the point of dropout. Descriptive analyses will be performed to describe the patient characteristics. Mean and standard deviation (std) or median and interquartile range for continuous characteristics and number and percentages for categorical characteristics will be determined. The relationship between treatment and outcome measures measured at 6 and 12 month follow up will be analysed with mixed three level linear or logistic regression, taking into account that the times of measurement (after 6 and 12 months) are clustered within patients, and patients within general practices. We will perform a

model with a random intercept and all other variables fixed. To test the effect of the intervention a model with time, group (intervention or control) and the interaction between time and group will be performed. Covariates included in the analyses will be age, sex, smoking status, education level, and social support. A value of  $p < 0.05$  will be considered statistically significant for all analyses, based on two-sided testing. Analyses will be performed using the Statistical Package for Social Sciences (SPSS, IBM Corp., Armonk, NY) version 25.

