### **6.3 Cost analysis**

We will perform two different approaches for cost analysis. First, we will assess total costs per capita per month (triple aim measure). Total costs will be calculated from a healthcare and a societal perspective. The healthcare perspective includes all costs covered by the healthcare budget, i.e. medication prescriptions, contact with care providers (GP, medical specialist, nurse, physiotherapist, dietician, podiatrist, occupational therapist), home care, hospital admissions, emergency department visits and rehabilitation. The costs from the

societal perspective include travel costs and costs of productivity loss due to absence from paid work. Total costs will be calculated per group and then divided by the number of patients per group and the length of follow-up to assess the total costs per capita per month. Data on healthcare utilization and medication prescriptions will be extracted from the electronic medical records of the participating general practices. Additional data on healthcare utilization as well as data on travel costs and absence from paid work will be retrieved from patients by questionnaire at 6 and 12 months. In addition, we will conduct a cost-effectiveness analysis in which cost-effectiveness will be assessed in terms of costs per quality-adjusted life years (QALY). QALYs will be based on the EuroQoI-5D (EQ-5D) utility values using the Dutch value set.

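### The cost per capita per month has no person-time rule: read plainly, questionnaire-only costs lost after dropout count as zero while their months stay in the denominator

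*Combined protocol and SAP*

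**What the plan says.** Section 6.3 plans two cost analyses. The first is a total cost per capita per month, from a healthcare and a societal perspective: "Total costs will be calculated per group and then divided by the number of patients per group and the length of follow-up". The second is a separate cost-per-QALY analysis. This point concerns the first.

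The costs come from two sources. Healthcare use and prescriptions come from practice records, which section 4.1 says are extracted at the end of follow-up. Additional healthcare use, travel costs and absence from paid work come from patient questionnaires. Section 6.3 puts these at 6 and 12 months; the cost-effectiveness table in section 4.3 lists the medical consumption questionnaire at baseline, 3, 6, 9 and 12 months.

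On follow-up and dropout:
- Section 2: the trial runs "with a follow-up time of 12 months". No other length is defined.
- Section 6: "Data from patients who discontinued follow-up will be included in the analysis up to the point of dropout".
- Section 4.6: "Patients who withdraw will be asked to fill the questionnaire for the measurement of the primary outcomes at 12 months". The cost questionnaire is not mentioned.
- Section 2.4 allows for 20% loss to follow-up overall and gives no rate by arm.

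No section gives a person-time rule, a censoring adjustment or imputation for costs.

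**The concern.** Section 6.3 applies one length of follow-up to a group total. Dropouts remain in the group, but their questionnaire-based costs stop. If the divisor is patients times 12 months, the unreported months enter at zero cost. The level of that cost component is then too low in both arms, and any true difference in it shrinks. If dropout differs between arms, the arm with more dropout gains an artificial saving. Section 4.2 says allocation cannot be masked from patients, so unequal dropout is plausible.

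The societal perspective is the more exposed, because the two items that 6.3 names for it, travel and productivity loss, come only from questionnaires. The healthcare perspective is exposed only through the additional care reported by questionnaire.

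For this measure, 6.3 also yields just one ratio per group. It states no interval and no allowance for clustering, although sections 6 to 6.2 model patients within practices. Cost effectiveness is one of the four aims in the Objectives.

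**Working it through.** The plan states no cost figure, cost SD or dropout rate by arm, so there is no figure of its own to reproduce. The check is an illustration.

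**Inputs from the plan:** follow-up 12 months (section 2); overall loss 20% (section 2.4); questionnaires at 6 and 12 months (6.3) or at 3, 6, 9 and 12 months after baseline (4.3).

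**Assumptions:** the same true monthly cost in both arms; dropout spread evenly over the year; a 25% against 15% split by arm, for illustration; each form covers the period since the previous one (the recall period is not stated).

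**Step 1: questionnaire-based part.** Let d be the dropout share and L the mean number of months lost per dropout. The share of true cost that is captured is 1 − d × L/12. If costs are captured up to dropout, L = 6. With forms at 3, 6, 9 and 12 months, a dropout in successive quarters loses 12, 9, 6 or 3 months, so L = 7.5. With forms at 6 and 12 months, a dropout loses 12 or 6 months, so L = 9.

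| Capture | L/12 | Captured share at d = 20% | Understated by | 25% against 15%, equal true costs |
|---|---|---|---|---|
| Up to dropout | 0.50 | 0.90 | 10% | 0.875/0.925 − 1 = −5.4% |
| Forms at 3, 6, 9, 12 months | 0.625 | 0.875 | 12.5% | 0.84375/0.90625 − 1 = −6.9% |
| Forms at 6, 12 months | 0.75 | 0.85 | 15% | 0.8125/0.8875 − 1 = −8.5% |

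With 20% dropout in both arms, the captured shares are equal and equal true costs still appear equal. A true difference in this part shrinks to 0.90, 0.875 or 0.85 of its size.

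**Step 2: total cost.** Let q be the share of total cost that only questionnaires capture; the documents do not give it. Records are taken as complete. With dropout at mid-year, the captured share of total cost is 1 − q × d × 0.5. For 25% against 15%:
- q = 0.5: 0.9375/0.9625 − 1 = −2.6%
- q = 0.25: 0.96875/0.98125 − 1 = −1.3%
- q = 0: no shift

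**Step 3: the alternative denominator.** Dividing each source's cost by the months that source covers returns the true monthly cost in every scenario, provided cost per month is unrelated to dropout. Time to dropout is not enough for questionnaire costs. With forms at 6 and 12 months and 20% loss, forms cover 0.85 of the months while time to dropout counts 0.90, and 0.85/0.90 = 0.944 still leaves a shortfall of about 5.6%.

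**The case against.** The strongest reply is that 6.3 leaves its denominator undefined and does not state a wrong one. It does not say that all enrolled patients are counted, nor that everyone is given 12 months, and no section says missing costs are set to zero. Section 6 treats follow-up as something that can end for a patient, so the length of follow-up could mean observed time. This stands as a limit on the point: the zero-cost result is the plain reading, not an explicit rule. But the plan gives no person-time rule, so a definition is needed either way. As step 3 shows, time to dropout would not fully repair the questionnaire part.

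A reader might infer that total costs are understated in both arms and that the arm with more dropout will look cheaper. The documents do not support that. Records extracted at the end of follow-up can stay complete after a patient stops returning forms. A bias between arms also needs unequal dropout, and the plan gives only an overall 20%. The 5% to 8.5% applies to one component whose share of total cost is unknown.

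A reader might also infer that costs are never analysed at patient level. That goes too far. Data are collected per patient, section 4.1.2 lists healthcare use among the secondary endpoints, and section 6.2 analyses those with clustering. Only the monthly cost measure is reduced to one ratio per group.

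**Conclusion.** The point holds for questionnaire-only costs, on the plain reading of 6.3. With the planned 20% loss spread evenly, that part is understated by about 10% if costs are captured up to dropout, 12.5% with forms at 3, 6, 9 and 12 months, and 15% with forms at 6 and 12 months. The last two figures assume that each form covers the time since the previous one.

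A spurious difference between arms is conditional on unequal dropout. At an assumed 25% against 15%, it is about 5% to 8.5% of the questionnaire part. With mid-year dropout, it is 2.6%, 1.3% or 0 of total cost as the questionnaire-only share goes from a half to a quarter to none. Record-based costs are unaffected if the records are complete. The point should be settled before cost data are seen. It does not touch the primary outcome.

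**What to change.** Replace the sentence in 6.3 with a rule by data source. For each source, divide the group's total cost by the sum of person-months that the source actually covers, then add the sources. For questionnaires, count the months covered by returned forms, not time to dropout. For records, count the months for which extraction is complete.

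Compare arms from patient-level costs, with an interval that respects practice clustering: a practice random effect, or a bootstrap that resamples practices.

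Add a sensitivity analysis that imputes missing questionnaire costs. Person-months remove the mechanical bias, but not bias that arises because dropouts have different costs from patients who stay.

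Reconcile the questionnaire times in sections 4.3 and 6.3, and state the recall period of each form, because these determine how many months a missing form loses.

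The cost is a few sentences and slightly more analysis work. No new data are needed.

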**Intervention:** a GDM programme including person-centered and holistic care. This programme will replace the SDM programmes for DM2, COPD and CVD that are currently used in the participating primary care cooperatives.

**Main study parameters/endpoints:** effectiveness will be evaluated by Quadruple Aim outcomes at baseline, at 6 months, and at 12 months follow-up by comparing changes in the intervention group with the comparator group. Patient experiences will be measured with the P3CEQ questionnaire. Population health will be measured with the PROMIS Global-10 questionnaire. Self-management will be measured with the Patient Activation Measure (PAM) score. Healthcare professional experiences will be measured with the MASGZ and the COPILOT questionnaire. Data for calculating costs and conducting a cost-effectiveness analyses will be measured by the Medical Consumption questionnaire and the EQ-5D questionnaire and by process outcomes such as the number and type of consultations and referrals, and duration of consultations from the Electronical Medical Files. At 12 months, a purposive sample of patients and professionals will participate in focus group interviews to collect information on experiences and facilitators and barriers for further implementation. Also, the competences needed by the healthcare professionals to provide personalised and integrated chronic care will be explored.

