#### 4.2 Randomisation, blinding and treatment allocation

The unit of randomisation will be the general practice (cluster). Practices will be randomised to intervention group (10 clusters) or comparator (5 clusters) in a 2:1 ratio. Five additional clusters will be randomised to the control group by a 2:1 ratio randomisation procedure in the parallel cluster RCT named EMBOSS in which the GDM programme will be adjusted to the needs of patients with low socioeconomic status (SES). In the EMBOSS cluster RCT the adjusted intervention will be provided to patients with low SES and at 12 months follow-up the effects will be compared to patients with low SES who have received care as usual. Figure 2 illustrates the combined randomisation procedure of both the OPTIMA FORMA and the EMBOSS cluster RCT.

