#### Cost-effectiveness

Category	Measurement instrument	Time
Medication	Data from medical records	12 months

Scheduled and unscheduled healthcare utilisation	Data from medical records	12 months
Referrals	Data from medical records	12 months
Costs	Data from medical records	12 months
	Medical consumption questionnaire	Baseline, 3, 6, 9, 12 months
	EQ-5D-5L	Baseline, 6, 12 months

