### **6.2 Secondary study parameter(s)**

The relationship between treatment and secondary outcome measures measured at 6 and 12 month follow up will be analysed with mixed three level linear or logistic regression, taking into account that the times of measurement (after 6 and 12 months) are clustered within patients, and patients within general practices. A model with time, group (intervention or control) and the interaction between time and group will be performed. Covariates included in the analyses will be age, sex, smoking status, education level, and social support

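### Section 6.3 gives the baseline Medical Consumption Questionnaire no role, so the cost comparison loses precision and is left open to chance baseline imbalance between few practices

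*Combined protocol and SAP*

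**What the plan says.** Section 6.3 sets out two cost approaches. The first is cost per head per month, from a healthcare and a societal perspective, obtained as a group average: "Total costs will be calculated per group and then divided by the number of patients per group and the length of follow-up". The second is a cost per QALY: "we will conduct a cost-effectiveness analysis in which cost-effectiveness will be assessed in terms of costs per quality-adjusted life years (QALY"). No model, covariate, practice term or baseline value is named for either.

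The questionnaire part of the cost data is "retrieved from patients by questionnaire at 6 and 12 months". The cost-effectiveness table in section 4.3 schedules the Medical Consumption Questionnaire at "Baseline, 3, 6, 9, 12 months".

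I find no other planned measure of care use before treatment. Section 4.1 takes physiological factors from records starting three months before baseline. It gives no such window for healthcare use or prescriptions, which are extracted at the end of follow-up.

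The Summary says that Quadruple Aim outcomes are evaluated "by comparing changes in the intervention group with the comparator group". The models of section 6.2 use the 6- and 12-month values, "taking into account that the times of measurement (after 6 and 12 months) are clustered within patients, and patients within general practices", and "Covariates included in the analyses will be age, sex, smoking status, education level, and social support". Prior care use is not among these covariates.

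Section 4.2 gives the number of practices: "Practices will be randomised to intervention group (10 clusters) or comparator (5 clusters) in a 2:1 ratio". It adds five control practices from the parallel EMBOSS trial. Randomisation is stratified by cooperative and by socioeconomic status of the practice population, not by care use.

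**The concern.** Cost-effectiveness is one of the four stated aims. Earlier care use usually predicts later care use, and the trial plans to measure it for every patient at baseline. As written, section 6.3 leaves that information out of the cost result.

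With only 15 to 20 practices, the groups can differ by chance in habitual care use and case mix. Part of such a difference would then be read as a saving or a cost of the programme. The confidence interval for the cost difference would also be wider than the planned data allow.

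This point concerns the cost side only. Baseline EQ-5D utility in the QALY calculation, and baseline scores in the models for the patient-reported outcomes, are separate matters.

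**Working it through.** The plan states no figure for the cost analysis, so there is none to reproduce. The inputs come from the sample size section (2.4). Its total of 680 can be reached from 35% v 20% with 138 per arm (276 in all). The design effect with 32 completers per practice is 1 + 31 × 0.03 = 1.93, so 276 × 1.93 = 532.7. Then 532.7 / 0.8 = 666, and 666 / 40 = 16.6, rounded up to 17 practices of 40.

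**Inputs**
- Practices: 10 v 5, or 10 v 10 with the EMBOSS controls (section 4.2).
- Patients per practice, m: 40 recruited, or 40 × 0.8 = 32 after 20% loss (section 2.4).
- ICC: 0.03, which the plan gives for the primary outcome. Its use for costs is an assumption.
- Correlation rho between baseline and follow-up cost: not in the documents; assumed 0.5, range 0.3 to 0.7.

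**Step 1. Chance difference at baseline, in patient-level SD units**

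SE = sqrt[(1 + (m − 1) × ICC) × (1/(k1 × m) + 1/(k0 × m))]

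| Practices | m = 32 | m = 40 |
|---|---|---|
| 10 v 5 | sqrt(1.93 × 0.009375) = 0.135 | sqrt(2.17 × 0.0075) = 0.128 |
| 10 v 10 | sqrt(1.93 × 0.00625) = 0.110 | sqrt(2.17 × 0.005) = 0.104 |

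With m = 32 and the ICC varied from 0.01 to 0.10, the range is 0.11 to 0.20 (10 v 5) and 0.09 to 0.16 (10 v 10). At ICC 0.03 and m = 32, the chance of a baseline difference above 0.2 SD is about 14% (10 v 5) or 7% (10 v 10).

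**Step 2. How much carries over**

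If the correlation is the same at patient and practice level, the expected shift in the unadjusted follow-up difference is rho × imbalance. For a 1-SE imbalance at rho 0.5:
- 10 v 5: 0.5 × 0.135 = 0.067 (m = 32) and 0.5 × 0.128 = 0.064 (m = 40).
- 10 v 10: 0.055 and 0.052.

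A simulation with 32 per practice returned carry-over slopes of 0.30, 0.51 and 0.71 (10 v 5) for rho 0.3, 0.5 and 0.7. The average shift over repeated randomisations was zero to within 0.002 SD, so there is no bias on average.

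**Step 3. Precision gained by adjustment**
- If variance falls at both levels, the remaining share is 1 − rho². The cut is 9%, 25% and 49% at rho 0.3, 0.5 and 0.7. At rho 0.5 the confidence interval is 1 − sqrt(0.75) = 13% narrower.
- If only patient-level variance falls, the cut is rho² × (1 − ICC)/(1 + (m − 1) × ICC). At rho 0.5 that is 0.25 × 0.97/1.93 = 12.6% (m = 32) or 0.25 × 0.97/2.17 = 11.2% (m = 40). The interval is then about 6% narrower.

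**Step 4. Would a change score do instead?**

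The variance of a simple change from baseline, relative to no adjustment, is 2(1 − rho): 1.4, 1.0 and 0.6 at rho 0.3, 0.5 and 0.7. Subtracting baseline therefore gains nothing at 0.5 and loses precision at 0.3. Baseline as a covariate does not have this drawback.

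Steps 2 and 3 show one effect from two sides. They should not be added together.

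**The case against.** The strongest reply is that randomisation already makes the unadjusted difference unbiased, and that chance imbalance belongs in its confidence interval. That stands. A reader might infer that baseline differences pass in full into the cost result, or that the result is biased. Neither follows: only the fraction rho is expected to carry over, and it averages out over randomisations. Selective uptake could make imbalance systematic, because practice nurses invite patients and allocation is not masked from practices. The documents do not show that it will, and section 2 has patients drawn from a random sample of those eligible.

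A reader might also infer that 6.3 rules out adjustment throughout. Group averaging is explicit only for the per-capita measure, and no formal comparison is attached to it. For cost per QALY the plan is silent, so adjustment is unspecified, not excluded.

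Nor can the imbalance be called large relative to a plausible cost effect. The documents give no expected cost effect, cost SD, cost ICC or correlation, and the trial is not sized for costs. Stratification by cooperative and socioeconomic status may also reduce the imbalance somewhat.

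Other text goes part of the way. Questionnaire-reported care use is a secondary endpoint in 4.1.2, so 6.2 puts it in a model with a practice level. That model still has no prior care use among its covariates, and it does not produce a cost difference. The Summary's wording on changes is general, and 6.3 does not carry it out for costs.

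Finally, follow-up costs rest largely on medical records, with the questionnaire as a supplement. The documents do not say that the baseline questionnaire covers travel or work absence. This limits the fix but does not remove the point.

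**Conclusion.** The point holds as one of precision and specification. Section 6.3 gives no role to a baseline measure of care use that the trial already plans to collect, and it leaves the estimation of cost per QALY unstated. If the ICC of 0.03 applies to costs, a chance baseline difference of 0.10 to 0.14 SD (1 SE) is ordinary, and an assumed 30% to 70% of it would carry into the unadjusted cost difference. At an assumed correlation of 0.5, adjustment cuts the variance by about 11% to 25%, depending on whether practice-level variance also falls. The size rests on the assumed ICC and correlation; the gap in 6.3 does not. The documents do not support a claim of bias. The change should be made before analysis, so that adjustment is not chosen after the costs are seen.

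**What to change.** In section 6.3:
- Estimate the between-group cost difference from patient-level costs, with a practice term and with baseline care use or cost from the baseline Medical Consumption Questionnaire as a covariate.
- Use this adjusted difference as the cost numerator of the cost per QALY.
- For the societal perspective, use the same baseline care-use covariate. Add baseline travel and absence costs only if the baseline questionnaire collects them.
- Keep the raw cost per head per month as a description.
- Reconcile 6.3 with the Summary's wording on changes, preferably through the covariate and not a change score. Also reconcile its 6- and 12-month questionnaire data with the five-point schedule in 4.3.

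The cost is analysis-plan wording and a patient-level cost model in place of a group average; no new data are needed. There are small downsides: baseline questionnaire use is an imperfect proxy for follow-up cost taken from records, and missing baseline values need simple imputation.
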